5.1 CONSENT PROCESS

All research personnel have up to date CITI Certification for Protection of Human Subjects and will keep this training current throughout the course of the study. Study participants will be recruited through local media outlets (e.g., craigslist, flyers, print ads, Facebook). Participants will complete an online redcap survey to determine initial eligibility. When participants click the link for this survey, they will see a brief description of the research study. Once participants have been determined to be initially eligible, they will be invited to participate in the consent process.

The consent process will take place via one of the following modalities: 1) Remote electronic consent (e-consent) via REDCap facilitated with a discussion over the phone, 2) Remote consent via doxy.me, or 3) in-person consent (in-person visit at start of Visit 1). Options 1 and 2 are functionally the same (remote teleconsent prior to attending Visit 1), but utilize different platforms (doxy.me vs. REDCap), and we have built in the option to use both platforms in case of technicality difficulties with one platform. During the COVID-19 restrictions, all consenting will be done remotely (not in-person). We have included the option for electronic consent to reduce the length of the first in-person visit, while still providing ample time for the consent process. During the teleconsent process, the participant and staff member will be able to talk with each other and review the consent form together. When participants sign the consent form (details below), the form can be downloaded by study staff and saved in a secure REDCap/Box folder (details below).

All participants will be provided with a hard copy and/or electronic copy of the consent form. Participants will be given time to review the consent documents, as well as a detailed overview of the consent documents by study staff. After participants have read the documents and the documents have been described by the study staff, participants will demonstrate that they understand key aspects of the study by verbally answering questions from study staff about participation (e.g., “Can you tell me what the risks of participation are?”). Participants will sign the consent form only after both the participant and the study staff member are confident that the participant understands their participation and the risks associated with participating. Consent/HIPAA signatures may be collected electronically. When consent is collected electronically in person, our study team has a combination laptop/tablet that will be used for the eProcess. No information will be stored locally on the laptop/tablet; all information will be stored securely in REDCap/Box folder if captured electronically. Instead of signing on paper, a participant will enter his/her name, date, and sign electronically (with mouse or finger) in REDCap. [name] will supervise all aspects of the recruiting process. During the COVID-19 restrictions, all consenting will be done remotely through Redcap.

5.2 SETTING

The Medical University of South Carolina will be the only study site. In-person lab sessions will take place in the Health Neuroscience Laboratory located at [name]. We currently use this lab space for a number of other lab-based studies. This space includes four testing rooms for conducting participant visits, and these testing rooms are ventilated to allow smoking/tobacco use inside the room. The lab also has a bathroom for collecting urine specimens, and a control room where staff can see and talk to participants while they complete smoking procedures in the testing rooms.

5.3 RECRUITMENT METHODS

Potential participants will be recruited from the Charleston, SC community using standard recruitment methods (craigslist, TV, radio, newspaper, social media) using IRB-approved flyers and ads. Potential participants will be directed to a REDCap screening questionnaire for determination of preliminary eligibility. All appropriate approvals will be obtained if/as needed prior to posting any flyers/advertising in the community.

5.4 SPECIMEN COLLECTION AND BANKING

We will collect spot urine samples at baseline and the follow up visit. These urine samples are collected for the purposes of pregnancy testing, and for testing urinary cotinine (the primary metabolite of nicotine) to assess nicotine exposure. Each specimen will be transferred to the Clinical Neurobiology Laboratory within the Institute of Psychiatry for the cotinine analysis. Specimens will be identified using participant ID, and the lab report will include the specimen ID, which can be linked back to the remainder of the participant data by the statistician. The report will be stored on a password protected server. Urine specimens will be destroyed after cotinine analysis.

5.5 MODIFIED PROCEDURES TO BE IMPLEMENTED DURING COVID-19 RESTRICTIONS:

After passing initial screening, all participants will be consented into the study through our established remote procedures via RedCap, instead of having the option to complete the consent process in person. All in-person screening questionnaires that can be administered over the phone prior to the visit will be completed over the phone (demographics questionnaire, physiological & medical history, & tobacco use history). Participants who are ineligible based on these questionnaires will be paid for the visit, but not required to come into the lab to complete the remaining screening assessments. If the participant is still eligible after completing these questionnaires, we will then schedule them to come into the laboratory to complete the remainder of the visit. For visits 2 and 3, we will complete any questionnaires remotely that we can complete remotely. For interview-administered questionnaires, we will call participants in advance of the visit and complete the questionnaire over the phone via interview with study staff. For questionnaires that are completed independently by the participant, we will send them a RedCAP link prior to the visit and request that they complete the questionnaires on their own. If participants fail to complete these questionnaires on their own or we are unable to reach them to complete the questionnaires, we will ask the participant to complete them at the visit in the lab.

Protocol version August 18, 2020

For all visits, participants will be called 24 hours prior to all visits to confirm they are not experiencing any symptoms of COVID-19. All participants for each visit will be required to wear a mask and remain six feet away from the research staff and others when possible. When staff and participants must interact (for CO collection and e-cigarette disbursement), at least six feet of distance will be maintained by placing materials on a desk/table six feet away from the participant and then staff stepping away while the participant approaches to retrieve materials. All surfaces will be sanitized prior to the visit and after the visit.

6 STUDY

Timepoints	Screening / Baseline	Lab Session 2 Reinforcement Session	Lab Session 3 Follow up Session
Assessments			
Informed Consent	X		
Demographics	X		
Carbon Monoxide	X	X	X
Pregnancy Test	X		
Physiological and Medical History	X		
Tobacco Use History	X		
Adverse Event Monitoring		X	X
Timeline Followback	X	X	X
Cotinine	X		X
Stages of Change	X		
Fagerstrom Test for Nicotine Dependence	X		X
Penn State Cigarette Dependence Index	X		X
Penn State Dependence –Assigned Product			X
Brief Wisconsin Inventory of Smoking Dependence Motives	X		X
Electronic Daily Diaries	Enroll→	→	→Unenroll
*Cigarette Evaluation Scale		X	
*Purchase Task (UB)		X	
*Perceived Health Risks (UB)		X	
*Product Evaluation Scale (IQOS)		X	
*Purchase Task (Cig + IQOS)		X	X
*Purchase Task (IQOS)		X	X
*Perceived Health Risks (IQOS)		X	X
Preference Task		X	X

7 RISKS AND BENEFITS

The research protocol calls for smokers to use an IQOS product. Participants are not required to use the product during the at-home sampling period but are asked to take four puffs of each product during the Lab Reinforcement Session. HTP are no more harmful than conventional cigarettes, and various studies suggest that they may offer reduced harm. Questionnaires and interviews are all non-invasive and involve minimal risk to study participants.

7.1 RISKS TO SUBJECTS

Potential risks are as follows:

- 1) Use of HTP
- 2) Concurrent Use of HTP and smoking
- 3) Potential for undermining cessation
- 4) Non-smokers in the home (i.e., children) experimenting with non-cigarette tobacco products
- 5) Loss of confidentiality

Use of HTP. HTP are not fully combusted, and therefore levels of carcinogens are markedly reduced, if not eliminated, comparable to trace levels seen in nicotine replacement products[2]². HTP contain reconstituted tobacco, and therefore, toxicant exposure appears to be greater than it is for exclusive use of e-cigarettes [2]. Thus, for current smokers who are provided with an HTP, such as IQOS, use of this product is less harmful than continuing to use their current tobacco product. We will verify smoking status and study onset, and thus, we will not provide an HTP to anyone to whom it would present increased risk.

There is little information about likely AEs for use of HTP or the IQOS product. In a randomized trial conducted by industry scientists, there were fewer AEs among smokers who were randomly assigned to switch to IQOS than among smokers who were randomly assigned to continue smoking their usual brand[4]. However, the incidence of cough was higher among the participants assigned to switch to IQOS (20%)[4].

Concurrent use of HTP and smoking. If smokers engage in dual use, the major concern will be intake of nicotine, and too much of it. Symptoms of nicotine intoxication include nausea, dizziness, headache, and stomachache[5]. In a randomized trial conducted by industry scientists, smokers who were randomly assigned to switch to IQOS sometimes used both IQOS and cigarettes, and there was no reported evidence of nicotine intoxication, nor were there any serious adverse events[4]. The bulk of the evidence surrounding these products suggests that smokers who engage in dual use with HTP are able to titrate their nicotine intake. That is, they reduce their use of one product when they increase use of another product in order to avoid excessive nicotine intake. In the same randomized IQOS trial discussed above, smokers who used both IQOS and smoked cigarettes did not have significantly changed exposure to nicotine [4]. Thus, it is unlikely that concurrent use of cigarettes along with the IQOS product would result in nicotine intoxication.

Undermining cessation. Another potential risk is that the sampling intervention will decrease rather than increase future cessation. We do not know of any studies to examine this research question for IQOS. All participants will be told at the outset that quitting use of all tobacco products

is best for their health, and that quitting smoking by switching to a less harmful product would improve their health.

Use of HTP among non-participants and non-smokers, including children. Whenever a product is given to a smoker to take home and use, there is potential that the product will be used by someone else, inclusive of non-smokers and even children. This would be the case for a local in-person study or a remote study. In [name] recently completed snus trial in which he mailed tins of smokeless tobacco to smokers all over the country, such "diversion" was not a problem, nor has it been observed in his ongoing R01 of e-cigarettes. We will verify smoking status at the study outset and will advise participants who receive HTP to keep them out of reach of children and pets.

Confidentiality. A final risk is breach of confidentiality.

2. Adequacy of protection against risks.

2.1 Informed consent. All research personnel have up to date CITI Certification for Protection of Human Subjects and will keep this training current throughout the course of the study. Study participants will be recruited through local media outlets in each recruitment city (e.g., craigslist, flyers, print ads, tv, Facebook). Participants will be directed to an online REDCap screening questionnaire for determination of initial eligibility. We have a system in place for REDCap to flag potential duplicate entries, ensuring we are able to exclude participants who might try to complete the screener multiple times to gain entry to the study. Participants who are determined to be eligible will be sent the informed consent document to review on their own before scheduling an informed consent teleconsent session or coming to the lab to review the consent document in person. During the consent session, study staff will review the consent document with participants, and answer any questions the participants may have. Participants will demonstrate that they understand key aspects of the study by verbally answering questions from study staff about participation (e.g., "Can you tell me what the risks of participation are?"). Participants will sign the consent form only after both the participant and the study staff member are confident that the participant understands their participation and the risks associated with participating. Consent signatures will be collected electronically during teleconsent or on our study tablet if in person. No information will be stored locally on the laptop/tablet; all information will be stored securely in REDCap. We will abide by all HIPAA regulations as set forth by our institution. [name] will supervise all aspects of the recruiting process.

2.2 Protection against risk.

Use of HTP. At screening, participants will be screened for general medical precautions by self-report (cardiovascular disease, seizure disorders), and all participants will be monitored for adverse events during the study period. We will clearly advise against use of any tobacco product during pregnancy and breastfeeding. Participants will be educated about potential risks of tobacco use, including risks specific to HTP, and concurrent use of these products with cigarettes. Any serious or unexpected adverse events will be reported to the IRB. The most likely adverse event (potential for nicotine overdose) is anticipated to be rare (<5%) and mild (mouth/throat irritation, cough, headache, nausea, headache), and will be handled quickly (i.e., advice to participant to reduce or stop HTP). Lab studies of toxin exposure (above) suggest that HTP confer no greater risk to health than do conventional cigarettes. It is unlikely that HTP users will become addicted to the product in the 1-week sampling period. All participants will be provided with cessation information (referrals to Quitline) as part of this study.

Concurrent use of HTP and smoking. Per above, the most common effects from too much nicotine are nausea, headache, and disturbed sleep. The sampling period is one week in duration,

and thus we do not expect sustained patterns of dual use. We will track adverse events at every study contact and will have a toll-free number available for participants to call if they experience an adverse event (AE). All study contacts will remind participants of this number. Participants will be encouraged to contact [name] as soon as possible for serious events. If they wish, they may contact their local MD or give the study physician permission to do so.

Undermining cessation. We emphasize that this is not a cessation trial, though we will collect various cessation outcomes. Nonetheless, it is possible that use of HTP will undermine quitting (though this would be contrary to existing literature). At study outset and at the end of the study, participants will be reminded that quitting all tobacco products is best for their health, although completely switching to a less harmful product is likely to improve their health.

Diversion of or IQOS. We will verify smoking status prior to enrollment in order to ensure that we do not provide IQOS to a non-smoker for whom these products would represent increased health risks. We will strongly advise participants that they are not to share the study product with others, and that they should store the product in a secure area that is out of reach of children and pets. We cannot directly assess any diversion/uptake from the perspective of adolescents, since that would require separate consent, and is a separate research question.

Confidentiality. We will use the participant's name only on the screening and informed consent/HIPAA documents and these will be kept in electronically in REDCap, a secure database. Instead of signing on paper, a participant will enter his/her name, date, and sign electronically (with mouse or finger) in REDCap. REDCap is a secure, password-protected database. Any research materials collected on paper will be kept in locked files at the Cancer Control Program of the Hollings Cancer Center, with limited access to the study personnel. All database files will include password protection to further ensure confidentiality.

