3) At-home sampling period and Follow-up Session: Participants will be provided with an IQOS product to take home with them for a one-week sampling period. Participants will receive the IQOS product and a supply of Heat Sticks. Participants will be instructed to use their assigned product as much as they would like over the week. Participants will continue to complete the daily electronic diaries during this time period and will report use of their assigned product. The primary purpose of the daily diaries is to capture daily tobacco use more effectively than retrospective recall of tobacco use at a lab session. Participants will return to the lab following the sampling period for a follow-up session to complete additional assessments and collect expired carbon monoxide. A urine sample will be collected for cotinine analysis at this follow-up session.

Compensation: Participants will receive \$25 for the screening visit, \$75 for the lab reinforcement session, and \$50 for the follow-up session (\$150 total). Participants can earn up to \$25 per week for the daily diaries (\$50 total). Participants who complete all sessions and all diaries can earn up to \$200. Participants who are not eligible at the screening visit will receive \$15 for their time. Participants who are not eligible do not receive the full \$25 payment for that visit because the visit will be shorter (no additional baseline measures).

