8 DEFINITION OF ENDPOINTS

Screening: A variety of questionnaires and assessments will be used for the purpose of determining eligibility. This includes a Demographics Questionnaire, expired breath Carbon Monoxide reading, Physiological and Medical History Questionnaire, urinary pregnancy test, and a detailed Tobacco Use History Questionnaire.

Baseline: For participants who have been determined to be eligible, additional baseline questionnaires will be administered including a Stages of Change Questionnaire which assesses a participant's interest in quitting, smoking dependence questionnaires including Fagerstrom Test for Nicotine Dependence, Penn State Cigarette Dependence Index, and the Brief Wisconsin Inventory of Smoking Dependence Motives.

Daily Diaries: Daily diaries will assess the number of cigarettes used each day, as well as the number of IQOS Heat Sticks used. We will assess which product (cigarette or IQOS) was preferred and which was used first each day. Participants will be enrolled in these daily diaries at the baseline session and will continue to complete them each day until the Follow up session when they are

unenrolled. The primary outcome obtained using the daily diaries is the average number of cigarettes smoked during the baseline and sampling weeks.

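### Does checking adverse events only at Sessions 2 and 3 contradict the promise of quick handling, and does a cited 20% cough rate contradict the under-5% figure?

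*Combined protocol and SAP*

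**What the plan says.** All references are to the combined protocol and SAP.

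- **Section 7.1, item 2.2 (Protection against risk), use of the product.** The text states that "all participants will be monitored for adverse events during the study period". It names possible nicotine overdose as the likeliest event, which "is anticipated to be rare (<5%) and mild (mouth/throat irritation, cough, headache, nausea, headache), and will be handled quickly", by advising the participant. No source is attached to the percentage.
- **Same item, concurrent use.** "We will track adverse events at every study contact and will have a toll-free number available for participants to call". Each contact is also to remind participants of that number, and they are encouraged to get in touch promptly about serious events.
- **Section 7.1, earlier paragraphs.** Knowledge of likely adverse events is described as scant. An industry randomized trial is cited for 20% cough among smokers assigned to switch to IQOS. The same trial is cited as showing no sign of nicotine intoxication when both products were used.
- **Section 6.** The row "Adverse Event Monitoring" is marked at Lab Sessions 2 and 3, not at Screening/Baseline.
- **Section 5, at-home period.** "Participants will return to the lab following the sampling period for a follow-up session".
- **Section 8, diaries.** The content described is consumption of both products, plus daily preference and order of use: "We will assess which product (cigarette or IQOS) was preferred and which was used first each day". No adverse event item is listed.
- **Section 5.5, COVID-19 procedures.** "participants will be called 24 hours prior to all visits to confirm they are not experiencing any symptoms of COVID-19".
- **Section 11.** Serious adverse events are reviewed before the participant's next visit. Deaths are notified at once, and research assistants discuss issues with their supervisor at least weekly.

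**The concern.** The device goes home at the end of Session 2, and Session 3 follows the sampling week. All home use therefore falls between the two marked checks. The planned handling is advice about ongoing use, yet the first scheduled check on that use comes when the week is over. The daily diary could close the gap, but its described content is tobacco use and product preference.

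That seems to leave a dilemma. If a diary counts as a study contact, section 8 leaves out the tracking that section 7.1 promises. If it does not, the normal schedule has no contact during the week at all.

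The percentage adds to the unease. Cough is among the symptoms listed for an event put below 5%, while the same section cites cough at 20%.

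At stake would be late detection of symptoms during home use, and adverse event data resting on unsolicited calls and one recall at the end of the week. The protocol itself prefers daily diaries to recall for tobacco use.

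**Working it through.** **1. Scheduled checks during home use.** Inputs: 10 participants and one week at home (section 5); monitoring at Sessions 2 and 3 (section 6).

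- Participant-days: 10 x 7 = 70. Adverse event checks marked in the schedule within them: 0.
- Delay from onset to the next marked check, with onset assumed equally likely on days 1 to 7:
  - Session 3 on day 7: (6+5+4+3+2+1+0)/7 = 21/7 = 3 days on average.
  - Session 3 on day 8: (7+6+5+4+3+2+1)/7 = 28/7 = 4 days on average.

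The arithmetic is right, but it measures time to the next marked visit. Time to detection is shorter whenever a participant calls, and the documents give no call rate from which to estimate it.

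**2. Do sections 6 and 7.1 conflict?** The table has three columns, all of them visits. It has no place to show activity between visits, so a missing entry there says little. The two marked visits are those from first exposure to IQOS onward; the unmarked one comes before any exposure. Section 7.1 covers the interval with the telephone line. Quick handling in that section describes the response once an event is known, which is advice to the participant. It does not set an interval between checks.

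**3. The diary and the COVID-19 call.** Section 8 defines endpoints and describes what the diary measures for them. It is not the diary form, so its silence does not show that an adverse event question is absent. Under COVID-19 restrictions a staff call falls about a day before Session 3. Its stated purpose is COVID-19 symptoms, but the rule in section 7.1 on tracking at each contact applies to it on a plain reading.

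**4. Serious events.** Review before the next visit is a latest limit. It permits review during the home week and does not fix review at Session 3.

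**5. The percentages.** The under-5% figure has no stated inputs, so it cannot be reproduced. What the two rates would mean among 10 people, by the exact binomial:

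| Rate p | Expected, 10p | P(at least 1) = 1 - (1-p)^10 |
|---|---|---|
| 5% (ceiling) | 0.5 | 0.401 |
| 20% | 2.0 | 0.893 |

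These rows would conflict only if both described the same event. The first is attached to possible nicotine overdose, with cough as one symptom. The second is cough from any cause among smokers assigned to switch, in a trial whose duration the protocol does not give. On overdose itself, the protocol reports from that trial no evidence of intoxication, which points towards rare.

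Ten participants could not settle the matter in any case. With 0 events in 10, the two-sided 95% upper limit is 1 - 0.025^(1/10) = 30.9%, which is above both rates.

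**6. What depends on either point.** Section 2.1 has no safety objective, section 8 no adverse event endpoint and section 9.2 no adverse event analysis. The sample size in section 9.1 rests on feasibility. No stopping rule uses the under-5% figure.

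**The case for a change.** The best case for acting is that the remedy is cheap. One question in a diary already sent daily, or one sentence saying that detection during the week relies on participants calling, would bring sections 6, 7.1 and 8 into plain agreement. A telephone line is passive, and mild symptoms such as cough may never prompt a call. A protocol that trusts diaries over recall for cigarettes could reasonably do the same for symptoms, above all for a product it describes as little studied. Calling an event the most likely at under 5%, a few paragraphs after citing another at 20%, also reads awkwardly.

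Part of this stands. Under the normal schedule, no staff-initiated adverse event query is described for the home week, and the scope and source of the percentage are unstated. Neither amounts to a contradiction. Whether a one-week pilot of 10 smokers using a commercially sold product needs active daily symptom queries is a matter of preference, and a telephone line plus a visit at the end of the week is a defensible choice. Staff told to track adverse events at each contact can apply that instruction without new text.

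**Conclusion.** The concern does not hold as an inconsistency, and no change to the plan follows. The marked checks do bracket the home week, with none across its 70 participant-days. But the schedule lists visits only, the risk section provides a route between them, and the limit on serious-event review allows earlier action. The under-5% and 20% figures describe different events, so the gap between them is unclear scope, not a demonstrated error.

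What remains is missing descriptive detail that study staff can fill sensibly. It touches no objective, endpoint, test, sample size or reporting threshold.

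This rests on three readings: that the telephone line operates throughout the home week, that the instruction to track at each contact is followed in practice, and that section 8 is not a full listing of the diary. If the last reading is wrong, detection during the week depends on participants calling. The adverse event record would then be less complete, but the planned comparisons would be unaffected.
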